14.2 Appendix 2: Guidelines for the treatment of alpelisib induced diarrhea

Mild to moderate diarrhea has been reported within the ongoing studies of single-agent alpelisib. In order to effectively manage diarrhea and mitigate the escalation in severity or duration of diarrhea, patient education as well as proper management of diarrhea is mandatory. The following section outlines the recommended algorithm for management and treatment of alpelisib induced diarrhea (Benson et al 2004; Kornblau et al 2000; Wadler et al 1998).

The algorithm for treatment for diarrhea management is based on (Wadler et al 1998; Kornblau et al 2000).

Patient history of diarrhea

At screening, the patient's history of diarrhea should be reviewed and the patient should be appropriately informed of potential study drug-induced diarrhea and its management:

- Review previous medical history of diarrhea within the last 12 months; laxative use, colon surgery, abdominal and pelvic irradiation, nocturnal diarrhea, pain, ulcerative colitis and other diarrhea-inducing diseases/conditions;
- Stop all diarrheogenic agents at screening if possible, otherwise exclude from trial;
- Instruct patients regarding risk of developing diarrhea;
- Perform baseline clinical/laboratory studies according to the trial protocol (e.g. one could rule out carrier state of Salmonella spp., Clostridium difficile, Campylobacter spp., Giardia, Entamoeba, Cryptosporidium which can lead to opportunistic infections in immunosuppressed patients);
- Explain the frequency of diarrhea and its relationship to NCI CTCAE grading (Table 14-4).

Table 14-4 NCI CTCAE version 4.03 grading of diarrhea for patients without colostomy

Toxicity	0	1	2	3	4
Diarrhea	None	Increase of < 4 stools per day over baseline	Increase of 4-6 stools per day over baseline	Increase of ≥ 7 stools per day over baseline; incontinence; hospitalization indicated; limiting self-care ADL	Life-threatening consequences; urgent intervention indicated
Diarrhea is	Diarrhea is defined as: A disorder characterized by frequent and watery bowel movements.				

First report of diarrhea

- Obtain history of onset and duration of diarrhea
- Description of number of stools and stool composition (e.g. watery, blood, mucus in stool)
- Assess patient for fever, abdominal pain, cramps, distension, bloating, nausea, vomiting, dizziness, weakness (i.e., rule out risk for sepsis, bowel obstruction, dehydration)
- Obtain medication profile (i.e., to identify any diarrheogenic agents) and dietary profile (i.e., to identify diarrhea-enhancing foods)

Proactively look for occurrence of diarrhea. If no problems occur, instruct the patient to call when a problem does arise.

Management of diarrhea

General recommendations:

- Stop all lactose-containing products, alcohol
- Stop laxatives, bulk fiber (e.g. Metamucil®) and stool softeners (e.g. docusate sodium, Colace®)
- Stop high-osmolar food supplements such as Ensure Plus® and Jevity Plus® (with fiber)
- Drink 8 to 10 large glasses of clear liquids per day (e.g. water, Pedialyte[®], Gatorade[®], broth)
- Eat frequent small meals (e.g. bananas, rice, apple sauce, toast)

It is recommended that patients are provided with loperamide tablets at the start of each cycle. Patients should be instructed on the use of loperamide at Cycle 1 in order to manage signs or symptoms of diarrhea at home. Patients should be instructed to start oral loperamide (initial administration of 4 mg, then 2 mg every 4 hrs (maximum of 16 mg/day) at the first sign of loose stool or symptoms of abdominal pain. These instructions should be provided at each cycle and the site should ensure that the patient understands the instruction. At the beginning of each cycle, each patient should be specifically questioned regarding any experience of diarrhea or diarrhea related symptoms. If symptoms were experienced, then the site should question the patient regarding the actions taken for these symptoms.

Intensive management of diarrhea must be instituted at the first sign of abdominal cramping, loose stools or overt diarrhea. Note that all concomitant therapies used for treatment of diarrhea must be recorded on the Concomitant Medications/Non-drug Therapies section of the patient record.

Loperamide is the first-line treatment of diarrhea (any Grade) in this recommended algorithm. Persistent symptoms may require the administration of high dose loperamide followed by treatment with second-line agents such as opium tincture and octreotide acetate, based on severity and duration of diarrhea and related signs/symptoms. Another first-line treatment for diarrhea is diphenoxylate hydrochloride/atropine sulfate. This medication may be used in place of loperamide however it is important to note that loperamide and diphenoxylate hydrochloride/atropine sulfate must not be used in conjunction with one another due to the risk of developing paralytic ileus. Upon treatment

with any antidiarrheal agents, the patient's response to treatment should be observed and appropriately documented in the source document and within the patient record.

Treatment of diarrhea CTCAE grade 1 or 2

Diarrhea CTCAE grade 1 or 2 will be treated with standard loperamide (initial at first administration 4 mg, then 2 mg every 4 hrs (maximum of 16 mg/day) or after each unformed stool).

12-24 hrs later:

Diarrhea resolved

- Continue instructions for dietary modification
- Gradually add solid foods to diet
- Discontinue loperamide after 12 hrs diarrhea-free interval

Diarrhea unresolved

Persisting diarrhea CTCAE grade 1 or 2 will be treated with addition of opium tincture or dihydrocodeine tartrate tablets/injections with monitoring of patients condition to rule out dehydration, sepsis, ileus) medical check and selected workup if patient does not need hospitalization (see section Diarrhea workup and additional test in the particular trial protocol). Observe patient for response to antidiarrheal treatment.

Persisting diarrhea CTCAE grade 3 or 4 may be treated with hospitalization, high dose loperamide (initial 4 mg, then 2 mg every 2 hrs) and addition of opium tincture (DTO) or dihydrocodeine tartrate tablets/injections, start of IV fluids and antibiotics as needed with monitoring of patients condition (to rule out dehydration, sepsis, ileus) medical check and workup (perform appropriate additional testing). Enteric acting steroids /systemic steroids may be given if clinically indicated for the management of colitis. Observe patient for response.

After 12-24 hrs:

Diarrhea resolved

- Continue instructions for dietary modification
- Gradually add solid foods to diet
- Discontinue loperamide and/or other treatment after 12 hrs diarrhea-free interval

Diarrhea unresolved

- If diarrhea still persisting (CTCAE grades 1 and 2), after 2x 24 hrs with high dose loperamide and opiates then admit to hospital and employ measures as for CTCAE grade 3 and 4 until diarrhea resolved.
- If diarrhea still persisting and progressed to CTCAE grades 3 and 4, employ measures described below.

Treatment of diarrhea CTCAE grade 3 or 4

Severe diarrhea CTCAE grade 3 or 4 may be treated with hospitalization, high dose loperamide (initial 4 mg, then 2 mg every 2 hrs and addition of opium tincture or dihydrocodeine tartrate tablets/injections, start of IV fluids and antibiotics as needed with monitoring of patients condition (to rule out dehydration, sepsis, ileus) medical check and workup (see section Diarrhea workup and additional test in the particular trial protocol). Observe patient for response.

After 12-24 hrs:

- If diarrhea persisting administer s.c. Sandostatin/octreotide (100-500 μg tid)
- Continue IV fluids and antibiotics as needed
- If diarrhea CTCAE grade 3 or 4 still persists patients should receive opium tincture or dihydrocodeine tartrate injections s.c. or i.m.
- If diarrhea CTCAE grade 3 or 4 is still persisting s.c. Sandostatin/octreotide (500-1000 μg TID) should be administered.
- To control and/or resolve diarrhea, next cycle of treatment should be delayed by 1 or 2 weeks. Treatment should be continued only when diarrhea resolved.

Diarrhea workup

Perform appropriate tests (Fine et al 1999).

Spot stool analysis

- Collect stool separating it from urine (special containers, analysis immediately, exceptionally freeze samples)
- Blood
- Fecal leukocytes (Wright's staining and microscopy) or
- Clostridium difficile toxin
- Fecal cultures including Salmonella spp., Campylobacter spp., Giardia, Entamoeba, Cryptosporidium (which can lead to opportunistic infections in immunosuppressed patients), plus Shigella and pathogenic E. coli enterotoxigenic, enterohemorrhagic etc., possibly Aeromonas, Pleisiomonas (if suspected exposure to contaminated water)

Endoscopic examinations

Endoscopic examinations may be considered **only if absolutely necessary**. The bowel is likely to be fragile with evidence of colitis and thus great care and caution must be exercised in undertaking these invasive procedures.

- Gastroscopy to obtain jejunal fluid re. bacterial overgrowth for cultures and biopsy of proximal jejunum to assess extent of inflammatory jejunitis
- Sigmoidoscopy reassessment of colitis. Biopsy: Histopathological examination of colonic mucosa and immunophenotyping may be performed to confirm the etiology of colitis.

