6.1.1.1 Alpelisib dosing

Alpelisib at a dose of 300 mg will be administered orally once daily on a continuous dosing schedule starting on cycle 1 day 1 in combination with fulvestrant (500 mg intra muscular), or letrozole (2.5 mg).

The investigator or responsible site personnel should instruct the participant to take the study drugs as per protocol (promote compliance). Drug accountability must be performed on a regular basis. Participants will be instructed to return unused alpelisib tablets to the site at the end of each cycle or at the time of discontinuation of study treatment. The site personnel will ensure that the appropriate dose of each study drug is administered at each visit and will provide the participant with the correct amount of drugs for subsequent dosing.

Alpelisib is dosed on a flat scale of mg/day and not by weight or body surface area. There will be no breaks between dosing cycles.

The following general guidelines should be followed for alpelisib administration:

- Patients should be instructed to take the dose of alpelisib once daily at approximately the same time each day after food (preferably in the morning), except on the days blood collection is scheduled at the clinic, at which time the patients should take their doses at the clinic at any later point of time.
- Alpelisib must be taken within 1 hour after a meal or snack. If, for any reason, a breakfast (or other meal) was not consumed, then the patient should take study treatment with a glass of water within 1 hour after a snack at any later point in time. If a dose of alpelisib is missed, it can be taken immediately after food and within 9 hours after the time it is usually administered. After more than 9 hours, the dose should be skipped for that day. On the next day, alpelisib should be taken at the usual time.
- Alpelisib should be taken with a glass of water. Tablets should be swallowed whole (tablets should not be chewed, crushed or split prior to swallowing). Tablets that are broken, cracked, or otherwise not intact should not be ingested.
- If vomiting occurs during the course of treatment, no re-dosing of the patient is allowed before the next scheduled dose. The occurrence and frequency of any vomiting during a treatment cycle must be noted in the adverse events section of the eCRF

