6.3.1.4 Alpelisib

For patients who do not tolerate the protocol-specified dosing schedule, dose adjustments are permitted in order to allow the patient to continue the study treatment. All dose modifications must be based on the worst preceding toxicity as graded by the NCI Common Terminology Criteria [NCI-CTCAE v4.03]. If the administration of alpelisib is interrupted for reasons other than toxicity, then treatment with alpelisib may be resumed at the same dose.

A maximum of 2 dose reductions of alpelisib from the recommended starting dose may be allowed before considering discontinuation of alpelisib treatment.

Please refer to Table 6-2 and Table 6-3 for guidance.

Table 6-2 Dose reduction sequential steps for alpelisib

Alpelisib dose level	Dose and schedule	Number of tablets & strength
Starting dose	300 mg/day continuously	1 x 200 mg tablet and 2 x 50 mg tablet
Dose level -1	250 mg/day continuously	1 x 200 mg tablet and 1 x 50 mg tablet
Dose level -2	200 mg/day continuously	1 x 200 mg tablet

Recommendations for dose reduction or dose interruption of alpelisib in the management of adverse reactions are summarized in Table 6-3. Adverse events for alpelisib are graded according to (Common Terminology Criteria for Adverse Events (CTCAE) v4.03 since this version is more objective with regards to hyperglycemia grading since it is based on laboratory values. Clinical judgment of the treating physician, including confirmation of lab values if deemed necessary, should guide the management plan of each patient based on individual benefit/risk assessment.

However, treatment must be discontinued as indicated in Table 6-3.

After treatment is resumed at a lower dose:

- If the same toxicity recurs with the same severity, then the next treatment re-initiation must resume at a lower dose irrespective of duration.
- Once the alpelisib dose has been reduced, no re-escalation will occur, even upon resolution of AE.

If a participant requires a withholding of alpelisib dose, the participant should continue combination drug, per investigator discretion. All scheduled assessments will continue to be performed as per protocol.

If administration of alpelisib dosing is held for more than 28 days, then alpelisib must be permanently discontinued. Grade 4 adverse events will lead to permanent discontinuation, irrespective of recovery time, unless otherwise specified. Patients requiring more than 2 dose reductions for alpelisib should be permanently discontinued.

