Worst toxicity – CTCAE Grade (value)	Dose Modifications for alpelisib
	 Exclude confounding factors like e.g. urinary tract infection.
	 Should consult with diabetologist, initiate or intensify medication with appropriate anti-diabetic treatment (see Grade 3), re-check within 24 hours.
	 If grade improves then follow specific grade recommendations
	 If FG is confirmed as > 500 mg/dl (27.8 mmol/L) and confounding factors could be excluded, permanently discontinue patient from alpelisib.

A diabetologist consultation should always be considered

For all grades: instruct patient to follow dietary guidelines according to local and/or institutional standards for management of diabetes mellitus (such as those provided by the American Diabetes Association) during the study, e.g. .small frequent meals, low carbohydrate content, high fiber, balancing carbohydrates over the course of the day; three small meals and 2 small snacks rather than one large meal

In cases where there is rapidly increasing serum glucose suspicious of severe clinical presentation and/or diabetic ketoacidosis) without obvious confounding factors and potentially need close observation and monitoring, a diabetologist should be consulted with consideration of potential hospitalization and close monitoring.

*specific recommendations please see Section 6.3.2.1.3.

Investigations (Hematologic)	
Neutropenia (ANC)	
Grade 1 (ANC < LLN - 1.5 x 10 ⁹ /L)	Maintain dose level
Grade 2 (ANC < 1.5 - 1.0 x 10 ⁹ /L)	
Grade 3 (ANC < 1.0 - 0.5 x 10 ⁹ /L)	Omit dose until resolved to ≤ Grade 1, then:
Grade 4 (ANC < 0.5 x 10 ⁹ /L)	
	 If resolved in ≤ 7 days, then maintain dose level
	If resolved in > 7 days, then ↓ 1 dose level
Febrile neutropenia	Omit dose until resolved, then ↓ 1 dose level
(ANC < 1.0 x 10 ⁹ /L, with a single temperature of ≥	
38.3 °C or a sustained temperature of ≥ 38 °C for more than one hour)	
Thrombocytopenia	
Grade 1 (PLT < LLN - 75 x 10 ⁹ /L)	Maintain dose level
Grade 2 (PLT < 75 - 50 x 10 ⁹ /L)	Walitain dosc level
Grade 3 (PLT < 50-25 x 10 ⁹ /L)	Omit dose until resolved to ≤ Grade 1, then:
	,
	 If resolved in ≤ 7 days, then maintain dose level
	If resolved in > 7 days, then ↓ 1 dose level
Grade 4 (PLT < 25 x 10 ⁹ /L)	Omit dose until resolved to ≤ Grade 1, then ↓ dose
	level
Investigations (Renal)	
Serum creatinine	
<2 x ULN	Maintain dose level
2 – 3 x ULN	Omit dose until resolved to ≤ grade 1, then:

Worst toxicity – CTCAE Grade (value)	Dose Modifications for alpelisib

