	 If resolved in ≤ 7 days, then maintain dose level If resolved in > 7 days, then ↓ 1 dose level
Grade 3 (> 3.0 – 6.0 x ULN)	Permanently discontinue patient from alpelisib
Grade 4 (> 6.0 x ULN)	Permanently discontinue patient from alpelisib
Investigations (Hepatic)	
Isolated total Bilirubin elevation	
Grade 1 (> ULN - 1.5 x ULN)	No dose adjustment is required. Initiate appropriate medical therapy and monitor as clinically indicated.
Grade 2 (> 1.5 - 3.0 x ULN)	 Interrupt dose until recovery to Grade ≤ 1 and resume at the same dose if resolved in ≤ 14 days or resume at the next lower dose level if resolved in > 14 days.
Grade 3 (> 3.0 - 10.0 x ULN)	Interrupt dose until recovery to Grade ≤ 1, then resume at the next lower dose level.
Grade 4 (> 10.0 x ULN)	Permanently discontinue.
Isolated AST or ALT Elevation	
Grade 1 (> ULN – 3.0 x ULN)	No dose adjustment is required. Initiate appropriate
Grade 2 (> 3.0 - 5.0 x ULN)	medical therapy and monitor as clinically indicated.
Grade 3 (> 5.0 - 10.0 x ULN)	 Interrupt dose until recovery to Grade ≤ 1, then resume at the next lower dose level.
Grade 4 (> 10.0 x ULN)	Permanently discontinue
Combined elevations of AST or ALT and total Bilirubin	Please see specific instructions in Section 6.3.2.2
Investigations (Gastrointestinal)	
Diarrhea is defined as: A disorder characterized by freq	uent and watery bowel movements.
Colitis is defined as a disorder characterized by inflamm	nation of the colon. (see also Appendix 2)
Grade 1 (Increase of < 4 stools per day over baseline; mild increase in ostomy output compared to baseline) OR	Maintain dose level but initiate appropriate medical therapy and monitor as clinically indicated
Asymptomatic colitis; clinical or diagnostic observations only; intervention not indicated	
Grade 2 (Increase of 4 - 6 stools per day over baseline; moderate increase in ostomy output compared to baseline)	Omit dose until resolved to ≤ Grade 1, initiate appropriate medical therapy then restart at same dose.
limiting instrumental Activities of Daily Living (ADL)	If diarrhea returns as ≥ Grade 2, then omit dose until resolved ≤grade1, then decrease 1 dose level
OR	
Abdominal pain; mucus or blood in stool	Initiate or intensify appropriate medical therapy and monitor as clinically indicated.
	For Grade 2 colitis consider additional treatment, such as steroids.

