Grade 3 (Increase of ≥7 stools per day over baseline; hospitalization indicated; severe increase in ostomy output compared to baseline; limiting self-care ADL)	Omit dose until resolved to ≤ Grade 1, then ↓ 1 dose level
OR	Manage according to local standard of care medical management, including electrolyte monitoring, administration of antiemetics and antidiarrhoeal

Worst toxisity CTCAE Grade (value)	Doca Madifications for alpaliaib	
Worst toxicity – CTCAE Grade (value)	Dose Modifications for alpelisib medicinal products and / or fluid replacement and	
Severe abdominal pain; peritoneal signs	electrolyte supplements as clinically indicated.	
	For Grade 3 colitis consider additional treatment, such as steroids.	
Grade 4 (Life-threatening consequences; urgent intervention indicated)	Discontinue subject from treatment.	
	Manage according to local standard of care medical management, including electrolyte monitoring, administration of antiemetics and antidiarrhoeal medicinal products and /or fluid replacement and electrolyte supplements, as clinically indicated.	
Investigations (Pancreatic)		
Pancreatitis		
Grade 2 (enzymatic elevation or radiologic findings only)	Omit dose until resolved to Grade ≤ 1, then resume treatment at ↓ 1 dose level. If toxicity recurs, permanently discontinue patient from alpelisib	
Grade 3	 Omit dose until complete resolution of symptoms 	
For patients deriving clinical benefit upon investigator's judgement:	and lipase resolved to Grade ≤ 1, then resume treatment at ↓ 1 dose level. Only 1 dose reduction is allowed.	
	 If recovery to ≤ Grade 1 is greater than 28 days, the patient must be discontinued from the study. 	
For other patients:	 If toxicity reoccurs, permanently discontinue patient from alpelisib 	
	Permanently discontinue patient from alpelisib	
Grade 4	Permanently discontinue patient from alpelisib	
Stomatitis/Oral mucositis (see also Appendix 3)		
Grade 1/Tolerable Grade 2	Maintain dose level	
	Non-alcoholic or salt water mouth wash	
Intolerable Grade 2 or Grade 3	First occurrence: hold until ≤ Grade 1 and ↓ 1 dose level (if stomatitis is readily manageable with optimal management, re-introduction at the same level might be considered at the discretion of the investigator).	
	Second occurrence: hold until ≤ Grade 1 and ↓ 1 dose level.	
Grade 4	Permanently discontinue patient from alpelisib	
Skin and subcutaneous tissue disorders		

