	 If rash resolves to ≤ G1 within 10 days systemic corticosteroid may be discontinued.
	Re-start alpelisib dose once rash /skin toxicity is fading but is no longer active (G1):
	at a reduced dose in case of first occurrence If rash/skin toxicity still active in up to 10% BSA
	after more than 14 days, continue oral

Worst toxicity – CTCAE Grade (value)	Dose Modifications for alpelisib
	corticosteroid for at least 48 hours upon re- challenge with alpelisib; if rash and/or pruritus do not reoccur within 48 hours after re-challenge with alpelisib, systemic corticosteroid may be discontinued
	For patients with symptoms like burning and/or pruritus add a non-sedating anti-histamine such as cetirizine once daily during daytime and a sedating anti-histamine such as diphenhydramine once daily at night. Antihistamine regimen should be continued for a minimum of 28 days after re-challenge with alpelisib.
Grade 4	Permanently discontinue patient from alpelisib
(any % BSA associated with extensive superinfection, with IV antibiotics indicated; life-threatening	Consult a dermatologist, strongly recommend documentation by photography and performing a skin biopsy if clinically indicated
consequences)	Treatment may follow guidelines for Grade 3 above with the exception of rechallenge.
	Additional measures may be taken as per local treatment guidance
Any Grade of Stevens-Johnson-Syndrome/Toxic Epidermal Necrolysis/Drug Reaction with Eosinophilia and Systemic Symptoms (DRESS) or other SJS/TEN/DRESS-like severe skin reactions	 Permanently discontinue patient from alpelisib treatment Consult dermatologist, strongly recommend documentation by photography and performing a skin biopsy if clinically indicated. Follow local treatment guidelines for SJS/TEN/DRESS
*"Active" skin toxicities: If there are no new lesions or ne appearance is changing color from red to pale or light b is not to be considered "active" any longer. Treatment re appearance of skin toxicity may fade slowly, over 10 da	rown, it is likely the skin toxicity has begun to fade and eduction can be considered for these areas. The
Investigations (Pulmonary disorders)	
Pneumonitis	
Please see specific instructions in Section 6.3.2.1.1	
Investigations (Metabolic)	
Asymptomatic amylase and/or lipase elevation (see	also Section 6.3.2.1.4)
Grade 1 (> ULN - 1.5 x ULN)	Maintain dose level
Grade 2 (> 1.5 - 2.0 x ULN)	Maintain dose level
Grade ≥ 3 (> 2.0 x ULN)	Omit dose until resolved to baseline, then

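### Appendix 2's dosing bullet for Grade 3 or 4 diarrhea does not match Table 6-3, and Section 6.3.1 cites the wrong table for mandatory stops (minor safety-consistency error)

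*Protocol*

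**What the plan says.** **Appendix 2 (Section 14.2).** The block on Grade 3 or 4 diarrhea covers hospital care, high-dose loperamide, opiates, fluids and octreotide. It closes with: "To control and/or resolve diarrhea, next cycle of treatment should be delayed by 1 or 2 weeks. Treatment should be continued only when diarrhea resolved". The two grades are not separated, and no dose reduction is mentioned.

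**Table 6-3 (Section 6.3.1.4).** The diarrhea and colitis heading carries the pointer "see also Appendix 2". At Grade 3, alpelisib is held until Grade 1 or better and then reduced by one dose level. At Grade 4 the action is "Discontinue subject from treatment", followed by supportive care under local standards.

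**Text of Section 6.3.1.4.** "However, treatment must be discontinued as indicated in Table 6-3". Also: "Grade 4 adverse events will lead to permanent discontinuation, irrespective of recovery time, unless otherwise specified".

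**Section 6.1.4.** For decisions on continuing treatment, it refers the reader to Section 6.3.

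**Section 6.3.1.** It says the events that require permanent discontinuation are those marked in Table 6-2 or listed in Section 7.1.5.

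**The concern.** A site managing severe diarrhea is pointed from Table 6-3 to Appendix 2. There it finds a study-treatment instruction covering Grades 3 and 4 together that describes delay and then continuation. For Grade 4, which Table 6-3 describes as life-threatening, the protocol elsewhere says treatment stops. For Grade 3, a site working from the appendix alone would resume at the same dose, whereas Table 6-3 requires a reduction. A reader who starts at Section 6.3.1 to find the mandatory stops is sent to a table that contains none.

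What is at stake is consistent safety conduct at sites. Sample size, power, hypothesis test and analysis definitions do not depend on this text.

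**Working it through.** **1. The two texts side by side**

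| Grade | Table 6-3 | Appendix 2 bullet | Match? |
|---|---|---|---|
| 3 | Hold to Grade 1 or better, then reduce one level | Delay next cycle 1 or 2 weeks; continue only when resolved | No: reduction missing |
| 4 | Discontinue | Same bullet as Grade 3 | No: Grade 4 stop missing |

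**2. Is the bullet about study treatment?** It speaks of the next cycle of treatment, so it reads as a dosing instruction and not as supportive care. The wording is awkward for a drug given daily with "no breaks between dosing cycles". That point adds little, since toxicity holds are provided for elsewhere and a short delay is one way to describe a hold.

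**3. Which text governs?** Section 6.1.4 sends continuation decisions to Section 6.3. Within it, Section 6.3.1.4 uses mandatory language and names Table 6-3. Appendix 2 calls itself a recommended algorithm. Table 6-3 therefore governs.

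**4. Is Appendix 2 an exception to the general Grade 4 rule?** That rule applies unless something else is specified. Table 6-3 supplies such exceptions itself: Grade 4 neutropenia allows resumption, and Grade 4 thrombocytopenia reads "Omit dose until resolved to ≤ Grade 1, then ↓ dose" level. Those rows explain the proviso without Appendix 2, and the Grade 4 diarrhea row specifies a stop.

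**5. Would the maximum-hold rule catch an error?** No. Section 6.3.1.4 requires permanent discontinuation after a hold of more than 28 days. A delay of 1 or 2 weeks is 7 to 14 days, which is shorter.

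**6. The Section 6.3.1 pointer.** Table 6-2 lists only the 300, 250 and 200 mg steps. Section 7.1.5 puts adverse events under reasons for which patients may be withdrawn; its mandatory list is pregnancy, death, and subject or guardian decision. Neither place states the Grade 4 stop. Table 6-3 does.

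**7. How often it could matter**

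Inputs: no Grade 4 diarrhea in the phase III study (Section 1.2.4.2); 284 patients on alpelisib plus fulvestrant there (Sections 6.4.1.1 and 6.4.3); Grade 3 or higher diarrhea in 7% (Section 1.2.4.2); 9 patients on treatment (Amendment 6 summary).

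- Exact 95% upper limit for 0/284: 1 − 0.025^(1/284) = 0.012905, or 1.29%.
- Expected Grade 4 cases among 9 patients: 0 at the point estimate; 9 × 0.012905 = 0.116 at the upper limit.
- Chance of at least one Grade 4 case at the upper limit: 1 − (1 − 0.012905)^9 = 0.110.
- Expected Grade 3 cases if the 7% applied: 9 × 0.07 = 0.63. With no Grade 4 reported, the 7% is taken as Grade 3.

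The missing dose reduction is therefore the mismatch more likely to arise in practice.

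**The case against.** The strongest reply is that the protocol already resolves the matter. Continuation is referred to Section 6.3, Section 6.3.1.4 says treatment must stop as Table 6-3 indicates, and the Grade 4 rule holds whatever the recovery time. The appendix bullet states a necessary condition for continuing; it does not grant a right to resume. In a joint block it can be read as operating for Grade 3 only, or for the partner drug, since Section 6.1.4 allows one study drug to continue after the other stops. A site that follows the cross-reference is already in Table 6-3, and the Grade 4 row gives its own supportive care.

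Most of this stands. A reader might infer that the protocol permits rechallenge after Grade 4 diarrhea, or that two instructions of equal force collide. The documents support neither inference, for the reasons just given.

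The contrast with rash also has limits. The Grade 4 rash row says "Treatment may follow guidelines for Grade 3 above with the exception of rechallenge", but it needs those words because it borrows the Grade 3 text. The Grade 4 diarrhea row borrows nothing from Grade 3.

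What the reply does not remove is that the bullet sits under a heading naming Grade 4, says nothing of the stop, and omits the reduction required after Grade 3. The pointer error in Section 6.3.1 has no defense beyond the correct reference in Section 6.3.1.4.

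**Conclusion.** The inconsistency is real in the current text and minor. Table 6-3 governs, so a careful reader reaches the right action at both grades. The appendix should still not say something different about dosing after a life-threatening event, or leave out a required dose reduction.

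The Grade 4 figures assume that the phase III rate applies to the remaining patients. Patients treated this long may have a lower rate, and some of the 9 may be on the partner drug alone. The 11% comes from a confidence limit and is the chance of any Grade 4 case. It is not the chance of wrongful rechallenge, which would also require a site to disregard Table 6-3 and Section 6.3.1.4. The Grade 3 figure of 0.63 rests on the same assumption and is illustrative.

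No sample size, power, test or analysis changes.

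**What to change.** 1. In Appendix 2, replace the next-cycle bullet with: *Grade 3: hold until Grade 1 or better, then reduce one dose level per Table 6-3. Grade 4: discontinue per Table 6-3, with no rechallenge; the supportive measures above may still be used.*
2. In Section 6.3.1, change the pointer for mandatory permanent discontinuation from Table 6-2 to Table 6-3.

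Leave the Grade 4 diarrhea row itself alone unless the sponsor first confirms whether only alpelisib or all study treatment stops. The column concerns alpelisib, but the row speaks of treatment in general, so new wording there would settle a question the protocol leaves open.

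The cost is two short wording edits, which can go into any later amendment. They need no new procedure, data or analysis.
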